## **Appendix 8. Treatment Recommendations for Symptoms of Infusion-Related Reactions Caused by Avelumab**

The following treatment recommendations for symptoms of avelumab infusion-related reactions may be modified based on local treatment standards and guidelines, as appropriate.

**For Grade 1 Symptoms:** (Mild reaction; infusion interruption not indicated; intervention not indicated):

- Decrease the avelumab infusion rate by 50% and monitor closely for any worsening.
- Remain at bedside and monitor patient until recovery from symptoms.

**For Grade 2 Symptoms:** (Moderate reaction; Therapy or infusion interruption indicated but responds promptly to symptomatic treatment (eg, antihistamines, NSAIDs, narcotics, IV fluids); prophylactic medications indicated for  $\leq 24$  hours):

- Temporarily discontinued the avelumab infusion.
- Treat based on emerging symptoms. Treatment may include:
  - Normal saline IV;
  - H1 blockers, such as diphenhydramine 25 to 50 mg IV (or equivalent);
  - H2 blockers, such as ranitidine 50 mg IV (or equivalent);
  - NSAIDs, such as ibuprofen 600 mg (or equivalent);
  - Meperidine 12.5 to 50 mg IV;
  - Corticosteroids, such as hydrocortisone 100 to 500 mg IV (or equivalent);
  - Bronchodilators.
- Remain at bedside and monitor patient until resolution of symptoms.
- Resume infusion at 50% of previous rate once infusion related reaction has resolved or decreased to at least Grade 1 in severity, and monitor closely for any worsening.

**For Grade 3 or Grade 4 Symptoms:** (Severe reaction; Grade 3: prolonged [eg, not rapidly responsive to symptomatic medication and/or brief interruption of infusion]; recurrence of symptoms following initial improvement; hospitalization indicated for clinical sequelae [eg, renal impairment, pulmonary infiltrates]; Grade 4: life-threatening consequences; urgent intervention indicated):

- Stop the avelumab infusion immediately and disconnect infusion tubing from the patient.
- Begin an IV infusion of normal saline, and treat the patient with one or more of the following:
  - Airway maintenance;
  - Oxygen;
  - Bronchodilators;
  - Epinephrine 0.01 mg/kg of a 1:1,000 (1 mg/mL) solution IM, up to a maximum dose of 0.5 mg;
  - H1 blockers, such as diphenhydramine 25 to 50 mg IV (or equivalent);
  - H2 blockers, such as ranitidine 50 mg IV (or equivalent);
  - Corticosteroids, such as hydrocortisone 100 to 500 mg IV (or equivalent).
- Remain at bedside and monitor patient until recovery from symptoms.
- Patients have to be withdrawn immediately from avelumab treatment and must not receive any further avelumab treatment.

2. INTRODUCTION

This SAP provides the detailed methodology for summary and statistical analyses of the data collected in study B9991003. This document may modify the plans outlined in the protocol; however, any major modifications of the primary endpoint definition or its analysis will also be reflected in a protocol amendment.

CCI

Statistical analyses will be performed using cleaned eCRF data as well as non-CRF data (i.e., tumor assessment results by the Blinded Independent Central Review (BICR), PK concentration, Anti-Drug Antibody (ADA), Neutralizing Antibody (nAb), biomarker data).

The primary analysis for progression-free survival (PFS) will include all data up to a cut-off date which is determined by the number of events required for the primary analysis of PFS in PD-L1 positive patients and a minimum follow-up of 12 months after the last patient is randomized.

The primary analysis for overall survival (OS) will include all data up to a cut-off date which is determined by the number of events required for the primary analysis of OS in PD-L1 positive patients.

The cut-off dates are determined once a data extract (before database lock) is available which indicates that the required number of events for PFS by Blinded Independent Central Review (BICR) assessment in PD-L1 positive patients and the minimum follow-up of 12 months, or the required number of events for OS in PD-L1 positive patients have occurred.

Due to data cleaning activities, the final number of events might deviate from the planned number. The data cut-off date will not be adjusted retrospectively in this case.

2.1. Study Objectives

Primary Objective

- To demonstrate that avelumab in combination with axitinib is superior to sunitinib monotherapy in prolonging PFS or OS in the first-line treatment of PD-L1 positive patients with advanced renal cell carcinoma (aRCC).

Secondary Objectives

- To demonstrate that avelumab in combination with axitinib is superior to sunitinib monotherapy in prolonging PFS in the first-line treatment of patients with aRCC unselected for PD-L1 expression;
- To demonstrate that avelumab in combination with axitinib is superior to sunitinib monotherapy in prolonging OS in the first-line treatment of patients with aRCC unselected for PD-L1 expression;
- To evaluate other measures of efficacy of avelumab in combination with axitinib and sunitinib monotherapy in the first-line treatment of aRCC patients;
- To evaluate progression-free survival on next-line of therapy (PFS2);
- To evaluate the overall safety profile of avelumab in combination with axitinib and sunitinib monotherapy in the first-line treatment of aRCC patients;

- To evaluate the population pharmacokinetics of avelumab and axitinib when administered in combination;
- To evaluate the time to treatment discontinuation/failure due to toxicity;
- To evaluate the proportion of patients who discontinued treatment due to toxicity;
- To evaluate candidate predictive biomarkers in pre-treatment tumor tissue that may aid in the identification of a patient subpopulation most likely to benefit from treatment with avelumab in combination with axitinib and sunitinib monotherapy;
- To assess the immunogenicity of avelumab when combined with axitinib;
- To evaluate the effects of avelumab in combination with axitinib and sunitinib monotherapy on patient-reported outcomes.

CCI

2.2. Study Design

This is a Phase 3, multinational, multicenter, randomized (1:1), open-label, parallel 2-arm study in which approximately 830 patients, including a minimum of 580 PD-L1 positive patients, are planned to be randomized to receive either avelumab in combination with axitinib or sunitinib monotherapy.

- Arm A: avelumab plus axitinib;
- Arm B: sunitinib.

Patients will be stratified according to ECOG PS (0 vs 1) and region (United States vs Canada/Western Europe vs the rest of the world).

Crossover between treatment arms will not be permitted.

3. ENDPOINTS AND BASELINE VARIABLES: DEFINITIONS AND CONVENTIONS

3.1. Primary Endpoint

- PFS based on BICR assessment per RECIST v1.1 for PD-L1 positive patients.

PFS is defined as the time from the date of randomization to the date of the first documentation of progressive disease (PD) or death due to any cause, whichever occurs first.

- OS for PD-L1 positive patients.

OS is defined as the time from the date of randomization to the date of death due to any cause.

3.2. Secondary Endpoints

3.2.1. Safety endpoints

- Adverse Events (AEs) as graded by National Cancer Institute (NCI) Common Terminology Criteria for Adverse Events (CTCAE) v4.03;

AEs will be graded by the investigator according to the CTCAE v4.03 and coded using the Medical Dictionary for Regulatory Activities (MedDRA);

- Laboratory abnormalities as graded by NCI CTCAE v4.03;
- Vital signs (blood pressure, pulse rate);
- Time to treatment discontinuation/failure due to toxicity;

Time to treatment discontinuation/failure due to toxicity is defined as the time from first dose of study treatment to discontinuation of study treatment (discontinuation of either avelumab or axitinib for arm A) due to an adverse event or death due to study treatment toxicity.

- Treatment discontinuation due to toxicity.

Treatment discontinuation due to toxicity is defined as the discontinuation of study treatment (discontinuation of either avelumab or axitinib for arm A) due to an adverse event or death due to study treatment toxicity.

3.2.2. Efficacy endpoints

- PFS by BICR assessment per RECIST v1.1 for patients unselected for PD-L1 expression.
- OS for patients unselected for PD-L1 expression
- PFS based on Investigator assessment per RECIST v1.1.
- Objective Response (OR), Disease Control (DC), Time to Tumor Response (TTR) and Duration of Response (DR) based on BICR assessment and based on Investigator assessment, per RECIST v1.1.

OR is defined as complete response (CR), or partial response (PR) according to RECIST v1.1, from the date of randomization until the date of the first documentation of PD. Both CR and PR must be confirmed by repeat assessments performed no less than 4 weeks after the criteria for response are first met.

DC is defined as CR, PR, non-CR/non-PD or SD. Both CR and PR must be confirmed by repeat assessments performed no less than 4 weeks after the criteria for response are first met. Criteria for SD and non-CR/non-PD must have been met at least 6 weeks after the date of randomization.

TTR is defined, for patients with an OR, as the time from the date of randomization to the first documentation of objective response (CR or PR) which is subsequently confirmed.

DR is defined, for patients with an OR, as the time from the first documentation of objective response (CR or PR) to the date of first documentation of PD or death due to any cause.

- Progression-Free Survival on next-line therapy (PFS2).

PFS2 is defined as the time from randomization to discontinuation of next-line treatment, second objective disease progression, or death from any cause, whichever occurs first.

- Measures of clinical outcome (PFS, OS, OR, DC, TTR, and DR) in biomarker-positive and biomarker-negative subgroups.

3.2.3. Patient reported outcomes

- FACT-Kidney Symptom Index (FKSI-19)

The FKSI-19 was developed to be part of the Functional Assessment of Chronic Illness Therapy (FACIT) system. It is an instrument specifically designed to be a stand-alone instrument to measure symptoms and quality of life in patients with advanced kidney cancer. It contains 19 questions, most of which overlap with the FACT-G questions (Rao et al. 2009). The FKSI-19 was developed in order to represent the symptoms and issues most important to people receiving treatment for aRCC.

A 9-item subscale of the FKSI known as the FKSI-Disease Related Symptoms subscale (FKSI-DRS) measuring advanced kidney cancer disease related symptoms was created using inputs from oncologists and patients (Cella 2005). This subscale includes the following 9 items: lack of energy, pain, losing weight, bone pain, fatigue, shortness of breath, coughing, bothered by fevers, and hematuria.

- EuroQoL 5-Dimension (EQ-5D)

The EuroQol EQ-5D is a 6-item patient-completed questionnaire designed to assess health status in terms of a single index value or utility score (The EuroQoL Group, 1990). There are two components to the EQ-5D; a Health State Profile which has patients rate their level of problems (none, slight, moderate, severe, extreme/unable) in 5 areas (mobility, self-care, usual activities, pain/discomfort, and anxiety/depression), and a Visual Analogue Scale (VAS) in which patients rate their overall health status from 0 (worst imaginable) to 100 (best imaginable). Published weights are available that allow for the creation of a single summary score (Rabin and de Charro, 2001). Overall scores range from 0 to 1, with low scores representing a higher level of dysfunction.

3.2.4. Pharmacokinetic endpoints

- PK parameters including trough concentrations (C_{trough}) of avelumab and trough concentrations (C_{trough}) and maximum concentrations (C_{max}) of axitinib

Table 2. PK Parameters to be Determined for Avelumab and Axitinib

Parameter	Definition	Method of Determination
$C_{\text{max}}^{\text{a}}$	Maximum observed plasma concentration	Observed directly from data
$C_{\text{trough}}^{\text{b}}$	Pre-dose concentration during multiple dosing	Observed directly from data
$C_{\text{max}}(\text{dn})^{\text{a}}$	Dose normalized C_{max}	$C_{\text{max}} / \text{Dose}$

^a C_{max} will be calculated only for axitinib

^b C_{trough} will be calculated for avelumab and axitinib

3.2.5. Immunogenicity endpoints

- Anti-drug antibodies (ADAs; nAb) of avelumab when in combination with axitinib.

3.2.6. Biomarker endpoints

- Tumor tissue biomarker status (i.e., positive or negative; based on, for example, PD-L1 expression and/or quantitation of tumor infiltrating CD8+ T lymphocytes as assessed by immunohistochemistry [IHC]; or based on expression of a gene/protein or group of genes/protein relating to, or indicative of an immune response within the periphery or tumor microenvironment).

Table 3. Biomarker Definition and Determination

Parameter	Definition	Method of Determination
PD-L1 expression	The number of PD-L1 positive cells and/or qualitative assessment of PD-L1 staining on tumor and inflammatory cells in regions of interest that are defined by tumor cell morphology and the presence or absence of CD8+ cells	Pathologist, assisted by image analysis
Tumor infiltrating CD8+ lymphocytes	The number of CD8+ cells per unit area and the percent of counted cells that are scored as CD8+	Pathologist, assisted by image analysis

CCI

CCI

3.4. Baseline Variables

3.4.1. Study drug, study treatment and baseline definitions

In this study, ‘**study drug**’ refers to avelumab or axitinib or sunitinib and ‘**study treatment**’ (or ‘**treatment arm**’) refers to one of the following:

- Arm A = avelumab plus axitinib;
- Arm B = sunitinib.

Determination of PD-L1 status

Determination of PD-L1 status will be performed retrospectively in a central laboratory.

PD-L1 status will be assessed using a validated PD-L1 IHC test kit manufactured under GMP specifications, in conjunction with a pre-specified scoring algorithm and cutoff defining PD-L1 positive versus negative status that will be established prior to initiation of scoring of PD-L1.

Start and end dates of study treatment

For Arm A

The date/time of first dose of study treatment in a combination arm is the earliest date/time of the first non-zero dose date/time for the study drugs in the combination.

The date/time of last dose of study treatment in a combination arm is the latest date/time of the last non-zero dose date/time for the study drugs in the combination.

For Arm B

The date/time of first dose of study treatment is the earliest date/time of non-zero dosing of the study drug.

The date/time of last dose of study treatment is the latest date/time of non-zero dosing of the study drug.

Definition of baseline:

Definition of baseline for efficacy and PRO analyses

The last measurement prior to randomization will serve as the baseline measurement for efficacy and PRO analyses. If such a value is missing (since per protocol the first PRO assessment is planned to occur prior to dosing on Cycle 1 Day 1), the last measurement prior to the first dose of study treatment will be used as the baseline measurement except for analyses of tumor assessments data where the baseline assessment would be considered as missing.

Definition of baseline for immunogenicity analyses

The last available assessment prior to the start of treatment with avelumab is defined as 'baseline' result or 'baseline' assessment. If an assessment is planned to be performed prior to the first dose of avelumab in the protocol and the assessment is performed on the same day as the first dose of avelumab, it will be assumed that it was performed prior to avelumab administration, if assessment time point is not collected or is missing.

Definition of baseline for safety analyses

The last available assessment prior to the start of study treatment is defined as 'baseline' value or 'baseline' assessment for safety analyses. If an assessment is planned to be performed prior to the first dose of study treatment in the protocol and the assessment is performed on the same day as the first dose of study treatment, it will be assumed that it was performed prior to study treatment administration, if assessment time point is not collected or is missing. If assessment time points are collected, the observed time point will be used to determine pre-dose on study day 1 for baseline calculation. Unscheduled assessments will be used in the determination of baseline. However, if time is missing, an unscheduled assessment on study day 1 will be considered to have been obtained after study treatment administration.

Patients who start treatment and discontinue from the study on the same day may have two different sets of data collected on study day 1 (one during study and one in the End of Treatment (EOT) visit). Data reported at the EOT visit are not eligible for baseline selection.

If a scheduled pre-dose measurement actually occurred post-dose, then the corresponding measurement will be treated and analyzed similar to an unscheduled post-dose measurement.

Baseline for RR and QT/QTc interval assessments will be derived from the visit where both RR and QT are not missing. Triplicate ECGs are collected in the study and the baseline for each ECG measurement is the average of the pre-dose replicate measurements on the baseline day. Unscheduled assessments will not be included in the calculation of the average. QTcB and QTcF will be derived based on RR and QT. The average of the replicate measurements will be determined after the derivation of the individual parameter at each time point.

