19. **Concomitant Medications/Treatments:** Concomitant medications and treatments will be recorded from 28 days prior to the start of study treatment and up to 90 days after the last dose of study treatment. All concomitant medications should be recorded in the CRF including supportive care drugs (eg, anti-emetic treatment and prophylaxis), the drugs used to treat adverse events or chronic diseases, and non drug supportive interventions (eg, transfusions). Arm B (Sunitinib Arm): From Cycle 2 onward, Days 15 and 29 concomitant medications collection may be performed by telephone call (eg, nurse) in a standardized form, unless the patient is visiting the site for other reasons. Arm A (this option is applicable only to patients on treatment with single agent axitinib, after they have visited the site every 2 weeks for additional 2 full cycles following avelumab permanent discontinuation): Days 15 and 29 concomitant medications collection may be performed by telephone call (eg, nurse) in a standardized form, unless the patient is visiting the site for other reasons.
20. **Patient-Reported Outcome Questionnaire:** FKSI-19 and EUROQoL 5-Dimension (EQ-5D) are to be administered on Day 1 (on randomization) of Cycle 1, and at Day 1 of each Cycle. PROs are to be administered always prior to any other test/procedure is performed.
21. **Randomization:** An interactive voice and web response system will be used for randomization to a treatment arm. Required information: site and patient identifiers and demographic information. Study treatment should begin within 3 days after randomization.
22. **Study Treatment:** Avelumab will be given as a 1-hour intravenous infusion every 2 weeks in a 6-week cycle. Axitinib will be given orally twice daily PO on a continuous daily dosing schedule. Sunitinib will be given orally 50 mg taken once daily, on a schedule 4 weeks on treatment followed by 2 weeks off (Schedule 4/2).
23. **Pharmacokinetics for axitinib:** In Arm A only, PK samples for axitinib (3 mL) will be collected at 2 hours post-dose on Day 1 of Cycle 1 and then at pre-dose and 2 hours post-dose for axitinib on Day 15 and 29 of Cycle 1. Details are outlined in [Section 7.3](#).

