### **5.1. Allocation to Treatment**

The investigator's knowledge of the treatment should not influence the decision to enroll a particular patient or affect the order in which patients are enrolled.

Once the patient has provided a signed Informed Consent Form (ICF) and has met inclusion and exclusion criteria, the Investigator or delegate will request the study treatment assignment using the Interactive Response Technology (IRT) system (interactive web-based response [IWR]/interactive voice response [IVR] system). Study treatment must start within 3 days after patient randomization.

The site personnel (study coordinator or specified designee) will be required to enter or select information including but not limited to the user's identification (ID) and password, the protocol number, the patient number, and the date of birth of the patient. The site personnel will then be provided with a treatment assignment and dispensable unit (DU) or container number when drug is being supplied via the IRT system. The IRT system will provide a confirmation report containing the patient number and DU or container number assigned. The confirmation report must be stored in the site's files.

There is a 24-hour-a-day, 365-days-a-year IRT helpdesk available for any questions or issues. The study-specific IRT reference manual will provide the contact information and further details on the use of the IRT system.

*Note:* The IRT is the source of the patient number. The IRT system will provide the patient number at the end of the first IRT patient transaction.

Qualified patients will be randomized in a 1:1 ratio to receive either avelumab in combination with axitinib (Arm A) or sunitinib monotherapy (Arm B).

Allocation of patients will be stratified according to ECOG PS 0 vs 1 and region (United States vs Canada/Western Europe vs the rest of the world). This stratified randomization will be centrally allocated across all centers via the IRT system.

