### **7.2.1. FKSI-19**

The FKSI-19 was developed to be part of the Functional Assessment of Chronic Illness Therapy (FACIT) system. It is an instrument specifically designed to be a stand-alone instrument to measure symptoms and quality of life in patients with advanced kidney cancer. It contains 19 questions, some of which overlap with the FACT-G questions. The FKSI-19 was developed in order to more comprehensively cover the items of interest in the quality of life measurement for aRCC patients. A 9-item subscale of the FKSI known as the FKSI-Disease Related Symptoms subscale (FKSI-DRS) measuring advanced kidney cancer

disease related symptoms was created using inputs from oncologists and patients. This subscale includes the following 9 items: lack of energy, pain, losing weight, bone pain, fatigue, shortness of breath, coughing, bothered by fevers, and hematuria. A parallel analysis from the FKSI validation study has been carried out to confirm the validity of this FKSI-DRS subscale. The FKSI-DRS has been a subscale of both the FSKI-15 and the FSKI-19. In validation studies, a change of 2-3 points has been established as the Minimally Important Difference (MID) for the FKSI-DRS.

The FKSI-19 questionnaire will be administered on the Cycle 1 Day 1, then at the beginning of the each treatment cycle as well as upon End of Treatment/Withdrawal. Beyond End of Treatment (ie, follow-up period), PRO assessments will be collected at the same time a tumor assessment is performed. The amount of time for a patient to complete the FKSI-19 questionnaire is estimated to be about 3-5 minutes.

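### The first PRO questionnaire may be completed after the open-label arm is known, so the baseline for the PRO analyses is not protected from knowledge of allocation

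*SAP*

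**What the plan says.** **Design and allocation.** SAP 2.2 describes the trial thus: "This is a Phase 3, multinational, multicenter, randomized (1:1), open-label, parallel 2-arm study". Under Protocol 5.1 the arm is disclosed at the randomization transaction: "The site personnel will then be provided with a treatment assignment and dispensable unit (DU) or container number". On the interval to dosing, the same section says "Study treatment must start within 3 days after patient randomization", and footnote 21 of the Schedule of Activities agrees.

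**Timing of the first questionnaire.** The Schedule of Activities has no FKSI-19 or EQ-5D entry at screening. Footnote 20 says the forms "are to be administered on Day 1 (on randomization) of Cycle 1, and at Day 1 of each Cycle", and adds "PROs are to be administered always prior to any other test/procedure is performed". Protocol 7.2.1 says "The FKSI-19 questionnaire will be administered on the Cycle 1 Day 1, then at the beginning of the each treatment cycle"; section 7.2.2 gives the same timing for EQ-5D.

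**Baseline rule.** SAP 3.4.1 takes the last value before randomization as the PRO baseline. If there is none ("since per protocol the first PRO assessment is planned to occur prior to dosing on Cycle 1 Day 1"), it takes the last value before first dose. For tumor assessments the same paragraph refuses this fallback and treats the baseline as missing.

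**Where the baseline is used.** SAP 6.3.2.4 to 6.3.2.7 use it for change-from-baseline summaries, time to deterioration (TTD, named the primary PRO endpoint in 6.3.2.1), time to improvement (TTI), the Cycle 5 improvement comparison, and as a covariate in the random coefficient models. The sensitivity analyses in 6.3.2.8 vary the point threshold and the assessment window, but not the baseline.

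**The concern.** A baseline should be fixed before the patient knows the arm. Randomization then makes the arms comparable at baseline, and any later difference can be read as an effect of assignment. Symptom and quality-of-life scores are self-reported. A patient who has just learned the assignment may rate symptoms better or worse out of optimism or disappointment. If this differs by arm, the difference enters every score measured against that baseline, even when the drugs have had no effect. In the random coefficient models it would mean adjusting for a covariate that allocation itself has influenced.

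At stake is the credibility of the PRO comparison, TTD in particular, because a threshold endpoint is sensitive to small shifts.

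**Working it through.** **1. Order of events.** No planned figure needs reproducing; the question is one of sequence.

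- Randomization call: the arm becomes known (Protocol 5.1).
- First dose, Cycle 1 Day 1: 0 to 3 days later (Protocol 5.1; footnote 21).
- First PRO form: Cycle 1 Day 1, before dosing and before other tests at the visit (footnote 20; SAP 3.4.1).

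If the call is on an earlier day than dosing, a form completed on the dosing day follows disclosure. If both fall on the same day, the form may come before or after the call. The rule that PROs precede other tests does not settle this, because it does not mention the call.

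**2. Effect of a shifted baseline on a mean.** If one arm's baseline is overstated by δ points, its mean change moves by -δ. In a model with baseline coefficient b, the adjusted arm difference moves by about -bδ.

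**3. Effect on the 3-point rule at one visit.** With true mean change μ, SD σ and baseline overstatement δ, taking change as normal:

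P(observed change ≤ -3) = Φ((-3 - μ + δ)/σ)

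The documents give neither μ nor σ, so both are assumed. With μ = -1 and σ = 5:

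| δ | Argument | P |
|---|---|---|
| -1 | -0.6 | 0.274 |
| -0.5 | -0.5 | 0.309 |
| 0 | -0.4 | 0.345 |
| +0.5 | -0.3 | 0.382 |
| +1 | -0.2 | 0.421 |

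**4. Range over the assumptions.** With no true change (μ = 0) and σ of 4, 5 or 6, the table gives P. In brackets is log(1 - P)/log(1 - P at δ = 0), a rough hazard-ratio equivalent if only one arm is shifted:

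| δ | σ = 4 | σ = 5 | σ = 6 |
|---|---|---|---|
| -1 | 15.9% (0.67) | 21.2% (0.74) | 25.2% (0.79) |
| -0.5 | 19.1% (0.82) | 24.2% (0.86) | 28.0% (0.89) |
| 0 | 22.7% | 27.4% | 30.9% |
| +0.5 | 26.6% (1.20) | 30.9% (1.15) | 33.8% (1.12) |
| +1 | 30.9% (1.44) | 34.5% (1.32) | 36.9% (1.25) |

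These are single-visit probabilities. TTD is the first crossing over repeated visits, so the bracketed ratios show scale and do not predict the trial's result. All the shifts shown are below the 2 to 3 point minimally important difference in Protocol 7.2.1.

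**The case against.** **The form may come first.** Footnote 20 ties the Day 1 form to randomization and puts it ahead of other tests, and 3 days is a maximum. A patient randomized and dosed on one day can complete the form before the call, and the SAP's first-choice rule then applies. This stands. A reader might infer that the baseline is always, or for most patients, obtained after allocation. The documents do not support that: they give neither the share randomized before Day 1 nor the order of form and call.

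**The timing is disclosed.** SAP 3.4.1 says openly why the preferred value may be absent. That is true, but no check of the consequence is planned.

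**Later forms are open-label too.** If an expectation effect persists, a baseline taken after allocation partly cancels it, whereas a pre-randomization baseline leaves it in. This is a fair point, but cancellation needs the effect to stay the same size over time, which cannot be verified. It does not make a post-allocation baseline preferable, since only a pre-randomization value is protected by randomization. What stands is that the fix removes one source of open-label PRO bias and leaves the rest.

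**A screening form has its own cost.** Screening may be up to 28 days before randomization, so the symptom score could be old. This favors same-day completion before the call.

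**It is too late to reorder the form.** Protocol 9.6 places the interim analyses after full randomization, and the current protocol has a schedule for the period after the third interim cutoff of 28-Apr-2020. The objection stands: for data already collected, only an analytic check can help.

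**Conclusion.** The point holds as a minor weakness in the PRO plan. The schedule permits the first form to follow disclosure of the arm, and the SAP accepts that form as the PRO baseline.

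The size of any shift is unknown, and so is its direction. On the main illustrative assumptions (normal change, mean -1, SD 5), a 0.5 to 1 point overstatement in one arm moves the single-visit decline rate from 34% to 38-42%, and an understatement of the same size moves it to 31-27%. The documents contain no evidence that any such shift occurred or which arm it would favor.

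Two wider readings should be resisted:

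- That every baseline in the trial is affected. Tumor data do not use the fallback, and safety and immunogenicity baselines have their own rules.
- That the main conclusions are at risk. PROs lie outside the four tested hypotheses, so PFS by BICR, OS and the type I error allocation are untouched.

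**What to change.** **Design wording.** Amend Schedule of Activities footnote 20 and Protocol 7.2.1 and 7.2.2 so that FKSI-19 and EQ-5D are completed before the randomization transaction, preferably the same day. The first-choice rule in SAP 3.4.1 then applies as written. The cost is a sequencing instruction to sites; no assessment is added, and the 336 PFS and 368 OS event targets do not change. This helps only patients not yet randomized, or a later trial using this template.

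**For patients already randomized**, add to the SAP:

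1. A tabulation by arm of first-form completion against randomization date, and time if recorded. Same-day forms without a time should be shown as order unknown.
2. Baseline FKSI-19, FKSI-DRS and EQ-5D scores by arm.
3. A TTD and TTI sensitivity analysis restricted to patients whose form was completed before allocation, if enough exist. If they do not, the report should say so and state the limitation.

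These steps use data already held and cost a few extra outputs. The restricted analysis loses precision and should be read as supportive only.
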